Given the potential non-inferiority of chemoradiation relative to radical cystectomy, clinical prediction of non-response to chemoradiation in terms of biomarkers would be of interest. However, there is paucity of predictive markers that can identify non-responders of chemoradiation. If predictive markers could be identified, patients might then be selected for the treatment most likely to benefit them, which would have the added advantage of maximizing overall cure rates and minimizing poor outcomes. Characterization of the genomic drivers of bladder cancer has been proposed for evaluating progression. Immunohistochemistry has been utilized with limited accuracy. A number of investigators have queried whether comprehensive genomic profiling of cancer-related genes could potentially assist in the selection of targeted therapies for patients with radiation refractory bladder cancer.³ As part of our pilot study, we propose to perform microarray gene expression profiling using Agilent long oligonucleotide (60 mers) technology to search for molecular alterations differing between responders and non-responders of chemoradiation with radical cystectomy as a reference.

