1.1. PRELIMINARY DATA

1.1.1. **Data on Chemoradiation:** The Kaplan–Meier plot in Figure 1 (copied from Reference 1) shows 348 patients with muscle invasive bladder cancer who underwent chemoradiation at Massachusetts General Hospital (MGH) by response (incomplete, complete). For clinical stage T2, three-year disease specific survival rates were 74% and 50% for patients who were complete and incomplete responders respectively.¹ The MGH Kaplan Meier curves for disease-specific survival suggest that response to chemoradiation may contribute to the non-inferiority of chemoradiation relative to radical cystectomy with regard to progression free survival in this study [Section 2, Specific Aim 1b].

[figure not shown]

Figure 1: Kaplan Meier plots for disease-specific survival following chemoradiation for all stratified by induction response status in the MGH study¹.

1.1.2. **Role of genome sequencing:** In a radiotherapy test cohort ($n = 201$), high tumor MRE11 expression (one of the candidate genes in our research) in patients receiving radiotherapy (RT) was associated with better cancer-specific survival compared with cystectomy [70% versus 55% 3-year cause-specific survival (CSS), $P = 0.021$]⁴, suggesting that MRE11 expression may play an important role with regard to predicting response to chemoradiation [Section 2, Specific Aim 2a]. Figure 2 shows the relevant plots copied from Reference 4.

[figure not shown]

Figure 2: Kaplan-Meier CSS curves for low and high MRE11 Radiation Therapy (RT) compared to cystectomy

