2. HYPOTHESIS AND SPECIFIC AIMS

Multiple prospective radiation therapy protocols have evaluated bladder-preserving chemoradiation therapy approach for muscle-invasive bladder cancer (MIBC), with radical cystectomy reserved for radiation failure. Aims of bladder preservation in MIBC are to offer a quality-of-life advantage and avoid potential morbidity or mortality of RC without compromising oncologic outcomes. Because of lack of level-1 evidence, oncologic equivalence of bladder preservation modality treatments compared with RC remains unknown.

2.1 HYPOTHESIS:

We hypothesized that chemoradiation is non-inferior to radical cystectomy for treatment of MIBC.

2.2 SPECIFIC AIMS:

SPECIFIC AIM 1a To determine and quantify quality of life in patients treated with radical cystectomy and chemo radiation therapy

1b To determine and quantify progression free survival and bladder-intact survival in patients treated with radical cystectomy and chemoradiation therapy,

SPECIFIC AIM 2a To evaluate genetic markers predicting response to chemoradiation by performing tissue RNA microarrays.

2b To assess the feasibility of conducting an adequately powered non-inferiority trial of the same design via recruitment rate, patient adherence to both treatment arm, and attrition.

2.3 STUDY DESIGN:

Our study will be a pilot, prospective, single-center, randomized non-inferiority trial comparing chemoradiation therapy to radical cystectomy. Patients diagnosed with muscle invasive bladder cancer after transurethral resection of bladder tumor and are surgical candidates will be randomized to either radical cystectomy (with neoadjuvant chemotherapy if suitable candidate) or chemoradiation.

Both treatment methods are considered “standard of care” recommended by the NCCN Clinical Practice Guidelines (http://www.nccn.org/professionals/physician_gls/pdf/bladder.pdf) in treating muscle invasive bladder cancer.

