to read and consider and ample opportunity will be given to answer any questions. The participant may decline to participate, decide to participate, or take the consent home to think about participating. A copy of the signed consent form will be provided to each participant.

The potential participant will then be scheduled for a TURBT (transurethral resection of bladder tumor) with the treating urologist, which may also be the study's principal investigator or co-investigator. TURBT is the standard of care which allows the treating urologist to formally assess the extent of disease progression and also to evaluate whether the candidate can be treated with both radical cystectomy and chemoradiation treatment. Potential participant will be approached to store any leftover tissue specimens, not needed for diagnosis, into the "GU Tissue Bank" (IRB HSC20050234H). The tissue collected will be processed per standard of care, and slides or tissue blocks may be accessed later for future use in correlative studies. The leftover specimens may be used for future research studies that may include genetic testing related to bladder cancer. This banking portion is optional and not required to be in the main study. If the participant declines to participate in the optional study, any leftover specimens will be permanently de-identified through the GUTB (05-234H).

The potential participant will then return to the clinic for a routine follow-up visit to review the TURBT results and discuss treatment options with the treating Urologist within 4 weeks post-TURBT. Final eligibility will be determined during the TURBT follow-up visit. If potential participant is eligible for the study, randomization will occur. The following section outlines study procedure during the visit.

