Categorical outcomes will be summarized with frequencies and percentages. Continuously distributed outcomes will be summarized with the sample size, mean, standard deviation, median, minimum and maximum. A consort diagram giving the number patients screened, the number of screen failures, the number randomized, the number lost to follow-up by reason, and the number completing the study by treatment arm will be created. In Aim 1a we will test the hypothesis that chemoradiation therapy is non-inferior to radical cystectomy with regard to change in quality of life at 36 months relative to baseline. In Aim 1b, we will test the hypothesis that chemoradiation is non-inferior to radical cystectomy with regard progression free survival and bladder intact survival. With regard to Aim 1a, assuming the 50% (p_2) of patients randomized to radical cystectomy and 60% (p_1) of patients randomized to chemoradiation will experience improvement in quality of life at 3 years relative to baseline and a 5% margin (Δ) of non-inferiority, this study would require $n=171$ subjects per group to attain 80% power for testing $H_0: p_1 - p_2 \leq \Delta$ versus $H_1: p_1 - p_2 > \Delta$ with $\alpha=5\%$. The non-inferiority of chemoradiation compared with radical cystectomy with regard to changes in quality of life (Aim 1a) will be assessed with Fisher's exact test. Progression free and bladder-intact survival (Aim 1b) will be summarized by treatment arm with Kaplan-Meier curves and supporting tabulations and non-inferiority will be assessed with a logrank test. The significance of treatment arm differences with regard to biomarkers (Aim 2a) will be assessed with t-tests or Wilcoxon tests. Pairwise correlations between biomarkers will be displayed overall and by treatment arm. Logistic regression will be used to find a best linear predictor of treatment arm in terms of multiple biomarkers. Biomarkers may be log transformed prior to analysis. Feasibility (Aim 2b) will be assessed with a new power and sample size calculation. If the logistic regression model fails in Aim 2a, random forests will be attempted. If the logrank test fails in Aim 1b, Fisher's exact test will be used. R (v3+, Vienna, Austria) or SAS (SAS Institute, Cary, North Carolina) software will be used throughout.

REFERENCES

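### The Aim 2a analyses target randomised treatment arm, so none of them can identify a marker of response to chemoradiation

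*Combined protocol and SAP*

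**What the plan says.** The purpose is stated three times, and each time it concerns response.

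- Section 2.2, Aim 2a: "To evaluate genetic markers predicting response to chemoradiation by performing tissue RNA microarrays".
- Section 1, last paragraph of the background: the profiling is meant to "search for molecular alterations differing between responders and non-responders of chemoradiation with radical cystectomy as a reference".
- Section 1.1.2: earlier MRE11 results are cited as "suggesting that MRE11 expression may play an important role with regard to predicting response to chemoradiation".

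Section 11 contains all the planned Aim 2a analyses:

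- "The significance of treatment arm differences with regard to biomarkers (Aim 2a) will be assessed with t-tests or Wilcoxon tests".
- Pairwise correlations between biomarkers, shown overall and by arm.
- "Logistic regression will be used to find a best linear predictor of treatment arm in terms of multiple biomarkers".
- "If the logistic regression model fails in Aim 2a, random forests will be attempted". No new outcome is named, so the target is still arm.

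On the data, Section 4.1 places TURBT and the approach for tissue banking before the post-TURBT visit. At that visit, "If potential participant is eligible for the study, randomization will occur". On banking it adds: "This banking portion is optional and not required to be in the main study". Section 9.5 limits the microarray to patients who agree to banking and names a goal of 50 candidate genes. Section 6 records biopsy and cytology results after induction, in the chemoradiation arm only.

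**The concern.** No analysis in Section 11 uses response as an outcome, a grouping variable or a covariate. Section 9.5 describes the assay and the genes but adds no response analysis. The outcome that Aim 2a needs is collected under Section 6 and then not used.

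The substitute cannot stand in for it. In tissue taken before randomisation, an arm difference can only be chance. Sections 9.5 and 9.8 do not restrict the samples to that tissue: they cover all bladder tumour specimens, and blood as well as tissue. In samples taken after treatment, an arm difference could be an effect of treatment. Neither is a marker of response, but either could be reported as one under the Aim 2a label.

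**Working it through.** The documents give no sample size, power or significance level for Aim 2a, so there is no planned figure to reproduce. The check has three parts.

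**1. What the arm analysis can show.** Section 3.3 makes the randomisation list the only basis for assignment, 15 per arm. Let X be the expression of a gene in pre-randomisation TURBT tissue. Then P(chemoradiation | X) = P(chemoradiation) = 15/30 = 0.5 for every X. The true coefficient of X in a logistic model for arm is 0 for every gene, and an arm test rejects at its nominal rate.

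**2. Size, by simulation.** X ~ N(0,1). In the chemoradiation arm, P(response) = 1/(1 + exp(-(a + bX))), with a set to give the stated response rate. There were 15,000 trials per cell, using two-sided 5% t-tests without adjustment. A trial with a group too small to test counts as no rejection. The values of b, the response rates and the number consenting to banking are assumptions, because the documents give none.

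| Gene | True AUC | Arm test, 15 v 15 | Response test, n = 15, at 50% / 65% / 70% / 80% responders |
|---|---|---|---|
| b = 0 | 0.50 | about 5% | – / 4.7% / 4.9% / – |
| b = 1 per SD | about 0.74 | about 5% | 34.7% / 32.6% / 30.3% / 22.8% |
| b = 2 per SD | 0.86-0.87 | about 5% | 75.2% / 70.1% / 66.5% / 50.8% |

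Across all cells the arm test rejected 4.6-5.4% of the time. If only 10 chemoradiation patients consent to banking, the response test for b = 2 rejects 46.5% (65% responders) or 42.2% (70%). A separate model (marker 2 SD higher in responders, 70% responders) gave 5.2% for the arm test. Its response test gave 87.7% among trials with at least two patients in each group.

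**3. What the right analysis can deliver with 15 patients.** The responder splits below are assumed.

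- *Power for one marker with a 1 SD difference* (exact Wilcoxon, unadjusted): about 37% at 8 v 7, 30% at 11 v 4 and 17% at 7 v 3.
- *Fifty genes.* At an assumed 5% each, 50 × 0.05 = 2.5 false positives are expected. Section 11 states no multiplicity handling. At 0.05/50 = 0.001, the first-rank Benjamini-Hochberg threshold, t-test power for the strong gene (b = 2, n = 15) falls to about 12%, 11% and 7% at 65%, 70% and 80% responders. For b = 1 it is about 2%.
- *Smallest possible two-sided exact Wilcoxon p*, 2/C(n, k): 2/6435 = 0.0003 at 8 v 7; 2/3003 = 0.0007 at 10 v 5; 2/1365 = 0.0015 at 11 v 4; 2/455 = 0.0044 at 12 v 3. The last two exceed 0.001, so at those splits that test could not declare a lone marker. The t-test has no such floor.
- *Precision.* Take an observed AUC of 0.76 at 11 v 4, with the 11 as the positive group. The Hanley-McNeil variance is [0.76 × 0.24 + 10(0.6129 - 0.5776) + 3(0.6564 - 0.5776)]/44 = 0.0175, so the SE is 0.132. On the logit scale the 95% CI is 0.43 to 0.93. With the 4 as the positive group it is about 0.37 to 0.94.
- *Ranking.* The best of 50 independent null genes has a median AUC of 0.86-0.88 at 8 v 7 (the median falls on a step of the discrete scale) and 0.91 at 11 v 4.

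**The case against.** The best defence is that the intent is on record. The background of Section 1 says that responders will be compared with non-responders, so an analyst has some basis for doing it. That is fair, and the defect is therefore confined to Section 11. But the background sentence names no test, outcome variable or analysis set, and Section 11 specifies a different analysis under the Aim 2a label.

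A second defence is that this is a 30-patient pilot with an exploratory aim, and the corrected analysis would seldom identify a marker. This also stands, as part 3 of the working shows: the 67-70% figure is for one pre-chosen strong gene without adjustment. It argues for labelling the analysis exploratory. It does not argue for analysing a variable that cannot bear on the question.

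A third is that the arm comparison serves the cystectomy reference mentioned in Section 1. A marker-by-arm comparison on an outcome measured in both arms could do so. A comparison of expression between arms does not.

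Finally, Section 4 lets patients be treated elsewhere with records only requested, so post-induction response may be missing for some of the 15. That is a real limit of the fix.

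**Conclusion.** The concern holds. The Aim 2a analysis is wrong as written, not merely short of detail: its tests and models target a randomised assignment, and no planned result bears on response. For pre-treatment tissue this follows from randomisation and needs no assumption. The simulated rejection rates (about 5% for the arm test; for the response test 30-33% with a moderate gene and 67-70% with a strong one, at 65-70% responders) rest on the assumed effect sizes, response rates and full banking consent. This should be fixed, because a stated aim otherwise goes unanswered. What is gained is agreement between aim and analysis; 15 patients will not yield a confirmed marker.

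**What to change.** In Section 11, replace the arm tests, the arm-prediction model and its random-forest fallback as the Aim 2a analysis with the following.

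- **Set and outcome.** Chemoradiation patients who consented to banking; outcome is the post-induction response recorded under Section 6.
- **Predictor.** Expression in pre-treatment TURBT tissue only.
- **Reporting.** Gene-by-gene effect estimates, for example AUC with 95% CI and the interval method stated, ranked and labelled hypothesis-generating. Give the number of genes examined and of patients contributing. Adjusted p-values are optional if no marker is to be declared.
- **Cystectomy arm.** Keep it as a descriptive reference, for example marker level against progression-free survival by arm. A within-arm analysis cannot separate a treatment-specific marker from a prognostic one.
- **Coding of response.** Section 5.2 speaks of complete response, while Section 6 groups T0, Ta and Tcis. Reconcile the two so that response is coded one way for analysis; this asks for no change to management.
- **Missing response.** State how patients without a post-induction evaluation are counted.

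The cost is an amendment to Section 11 and analyst time. No new assessment is needed, although records from outside centres may have to be pursued. At most 15 patients contribute, fewer if some decline banking, and a high rank alone proves nothing.

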9. DATA COLLECTION & STUDY EVALUATIONS

Medical records will be reviewed prior to “Baseline Study Visit” to confirm study eligibility. After obtaining consent, socio-demographic data will be collected through chart review and interviews. Clinical data that will be collected include but not limited to bladder cancer treatment history, tumor characteristics, stage, laboratory results, medications and co-morbidity.

Study team member or clinic staff will measure height, weight, and vital signs at each specific study time point. Research blood will be drawn at each study time point. Blood and tissue samples may be banked under the optional study (HSC20050234H GU Tissue Bank). For those participants who declined to participate in the optional study, any leftover samples will be permanently de-identified through the GU Tissue Bank (HSC20050234H) honest broker system. At the close of this study, all biological materials collected will be rolled into HSC20050234 GU Tissue Bank.

9.1 Feasibility: We will report recruitment, visit dates, adherence, attrition rates and compliance with randomization for each arm of the study

9.2 Bladder-intact survival: We will report proportion of patients who failed chemoradiation and required salvage cystectomy

9.3 Quality of life: A self-assessment questionnaire using the European Organization for Research and Treatment of Cancer (EORTC) QLQ- C30 and FACT-Bladder will be used for QOL assessment at baseline, 3, 6, 9 and 12 months.⁸

9.4 Progression free survival: This will be measured from the date of finishing chemoradiation or radical cystectomy to the date of first documentation of progression. Progression will be determined using RECIST 1.1 criteria by the treating physician based on radiographic or pathologic evidence of disease progression, or death from disease. Any documented recurrence will be considered progression.⁹ The date of progression will be recorded.

9.5 Candidate gene expression analysis: For the participants who have consented to be part of the optional study (“GU Tissue Bank HSC20050234H), a microarray analysis will be performed on all bladder tumor specimens using Agilent Technologies (Agilent SurePrint G3 Human Gene Expression 8x60K v2) Microarray. Goal is to study the landscape of 50 important candidate genes, which are involved in bladder cancer (for example-BRAF, KRAS, EGFR, FGFR).

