9.6 Activities of Daily Living (ADL) scores: This will be measured at baseline, and during all subsequent follow-up visit (i.e. 3, 6, 9 And 12 months) using Activities of Daily Living QOL Questionnaire using Katz Index of Independence in Activities of Daily Living (ADL).¹⁰

9.7 Retrospective screening & chart review: We will screen and review charts of “potential participant” retrospectively using the latest approved eligibility criteria and study schema to determine:

1. the number of “would-be potential participants”
2. the number of those who were initially deemed eligible and was truly eligible after TURBT
3. the number of those who were initially deemed eligible but was ultimately ineligible after TURBT

4. rationale for ineligibility

The retrospective screen & chart review will start from the date when the study was first approved by the IRB (i.e. April 15, 2016) until present time. Data including but not limited to medical record number, initials of name, gender, race, ethnicity, TURBT result, age at time of treatment, treatment received, date of treatment, eligibility status for the study, and rationale if deemed ineligible, will be captured. We do not intend to contact these patients for study enrollment since they would've received treatments for their diagnosis already. Our intention for this retrospective data collection is that it will provide further insight and information on the potentiality of chemoradiation as treatment modality for patients with specific bladder cancer diagnosis. We need to capture this data in order to represent total population of patients screened, thereby determining the denominator of the study population.

9. 8 Outline of Captured Data

Outcome of Interest	Measure	Method of Assessment
Demographics		Self-report questionnaire
Health History including height, weight, and vital signs		Physical exam, review of EPIC
Study Processes		
recruitment rate adherence attrition feasibility bladder intact survival safety		
Outcomes of interest		
Quality of Life	EORTC	Self-report questionnaire
	FACT-BI	Self-report questionnaire
ADL	Katz ADL	Self-report questionnaire
Progression free survival	RECIST 1.1	Physician assessment
Candidate gene expression	Candidate genes	Laboratory analysis of blood and tissue

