10.4 Assuring Compliance with Protocol and Data Accuracy

As with all studies conducted at CTRC, the PI has ultimate responsibility for ensuring protocol compliance, data accuracy/integrity and responding to recommendations that emanate from monitoring activities. Source verification of data will be performed every twelve week. Protocol compliance, data accuracy and reporting of events is further ensured by an annual audit conducted by the Data Safety Officer, whose audit report is shared with the PI, the research team, and will be reviewed by the CTRC DSMC.

11. STATISTICAL CONSIDERATIONS:

For this pilot non-inferiority study, we aim to randomize **30** evaluable patients (**radical cystectomy: n=15, chemoradiation: n=15**).

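### Section 11 assesses Aim 2b only by a new sample size calculation with unstated inputs, and does not tie recruitment, adherence and attrition to the feasibility conclusion

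*Combined protocol and SAP*

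**What the plan says.** Section 2.2 sets Aim 2b as assessing whether an adequately powered non-inferiority trial of the same design is feasible, "via recruitment rate, patient adherence to both treatment arm, and attrition".

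Three other places provide for the data:

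- Section 9.1, on feasibility: "We will report recruitment, visit dates, adherence, attrition rates and compliance with randomization for each arm of the study".
- Section 9.7 adds a retrospective chart review of screened patients, "thereby determining the denominator of the study population".
- Section 11 promises a CONSORT diagram that includes "the number randomized, the number lost to follow-up by reason, and the number completing the study by treatment arm will be created".

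For the analysis of Aim 2b, Section 11 has one sentence: "Feasibility (Aim 2b) will be assessed with a new power and sample size calculation". It does not say which quantities are updated from the pilot and which are kept from the existing calculation. The existing calculation, for Aim 1a, rests on assumed rates of quality-of-life improvement of 50% (cystectomy) and 60% (chemoradiation), a 5% margin, 80% power and alpha of 5%, and gives 171 per group. The pilot randomizes 15 per arm.

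**The concern.** The stated method does not answer the stated aim. A required sample size says how large the next trial must be. It does not say whether patients accept randomization between cystectomy and bladder preservation, stay with the assigned treatment, or remain under follow-up to 36 months. Section 1 gives feasibility data for a larger trial as the purpose of the pilot, so this is a central aim.

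The open inputs add a second problem. Section 11 already has a calculation from assumed rates, so a natural reading of a new one is that it uses the rates seen in the pilot. Nothing in the text rules that out. At 15 per arm, the result would then depend heavily on chance.

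**Working it through.** **Inputs, from Section 11:** p1 = 0.60 (chemoradiation), p2 = 0.50 (cystectomy), margin 0.05, power 80%, 15 per arm. Section 11 gives alpha as 5% without saying one- or two-sided.

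**Step 1: reproduce 171.** The formula is n per group = (z_alpha + z_power)² × [p1(1−p1) + p2(1−p2)] / (p1 − p2 + margin)².

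- One-sided 2.5%: (1.960 + 0.842)² = 7.849, so 7.849 × (0.24 + 0.25) / 0.15² = 170.9, that is 171. This matches the plan.
- One-sided 5% gives 135.

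The match requires one-sided 2.5% and a bound of −5 points. Read literally, the written hypotheses place the bound at +5 points and would give 1,539. That is a separate issue, and the work below uses the version that gives 171.

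**Step 2: recalculate with the pilot's observed rates (assumed use).** The standard error of the difference is √(0.24/15 + 0.25/15) = 0.181. The 95% range of the observed difference is therefore about 10 ± 35 points, or −25 to +45. Put into the formula, single patients move the result a long way:

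| Improved, chemoradiation v cystectomy | Observed difference + margin | n per group |
|---|---|---|
| 7/15 v 8/15 | −0.067 + 0.05, below 0 | none |
| 8/15 v 8/15 | 0.050 | 7.849 × 0.4978 / 0.0025 = 1,563 |
| 9/15 v 8/15 | 0.117 | 7.849 × 0.4889 / 0.01361 = 282 |
| 9/15 v 7/15 | 0.183 | 7.849 × 0.4889 / 0.03361 = 114 |

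Exact binomial enumeration over all outcomes, with true rates of 60% and 50%, gives:

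| Setting | Lower quartile | Median | Upper quartile | No finite n |
|---|---|---|---|---|
| 15 per arm, one-sided 2.5% | 56 | 114 | 1,563 | 23% |
| 15 per arm, one-sided 5% | 44 | 90 | 1,231 | 23% |

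At one-sided 2.5%, only 29% of pilots return a size between half and double 171. If dropout left 12 evaluable per arm (an assumption), 16% would do so and 24% would give no finite n.

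**Step 3: recalculate with the planned difference kept.** Hold the 10-point difference and 5-point margin, so the denominator stays at 0.0225, and update only the control rate over an observed 25% to 75%:

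- Control 25%: 7.849 × (0.2275 + 0.1875) / 0.0225 = 145.
- Control 45%, the maximum: 7.849 × (0.2475 + 0.2475) / 0.0225 = 173.
- Control 75%: 7.849 × (0.1275 + 0.1875) / 0.0225 = 110.

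The range is about 110 to 173 per group.

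**Step 4: what the pilot can say about the aim's own measures.** The counts are illustrative. Exact (Clopper-Pearson) 95% intervals are:

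- 24/30 adherent: 61% to 92%.
- 12/15 adherent in one arm: 52% to 96%.
- 6/30 lost: 7.7% to 38.6%. Inflating 171 for that loss gives 171/0.923 = 186 to 171/0.614 = 279 per group.

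**The case against.** Three stronger readings are tempting, and the documents do not support them.

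- *Recruitment, adherence and attrition have been dropped in favour of a power calculation.* They have not. Section 9.1 reports them by arm, Section 9.7 builds the screening denominator, Section 9.8 lists them as captured data, and the CONSORT diagram shows patient flow. The gap is that these summaries carry no precision and are not connected to the Aim 2b conclusion.
- *A pilot of this size cannot give a usable recalculated size.* That follows only if the treatment difference is re-estimated, which Section 11 does not say. Step 3 shows a recalculation that stays in a usable range.
- *A go/no-go decision will rest on chance.* No such decision rule appears anywhere in the protocol.

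It is also fair to say that a sample size calculation belongs in Aim 2b, because the aim concerns a trial with adequate power. Whether such a trial is feasible depends on the required number set against achievable recruitment and retention. This stands, and it is why the calculation should be kept as a supporting step.

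A further objection is that the proportions are imprecise too: 12/15 has an interval 44 points wide. That also stands. But those intervals concern the quantities the aim names, and they show their uncertainty openly. A single recalculated size does not.

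**Conclusion.** The concern holds as a mismatch between aim and method, together with unstated inputs. Section 11 assesses Aim 2b only by a sample size calculation, and the measures that define the aim are described elsewhere without precision or a link to its conclusion.

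The size of the second problem is conditional. If the pilot's observed difference is used, the recalculated size is too unstable to plan on. That result assumes true rates equal to the planned 60% and 50%, no dropout, and the one-sided 2.5% and −5-point bound inferred from 171. The instability remains at one-sided 5%. If the planned difference is kept, the problem does not arise. The text leaves both routes open, and this should be corrected before the analysis.

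**What to change.** Reword the Aim 2b sentence in Section 11 to say that:

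1. Feasibility is assessed by recruitment rate, adherence by arm and attrition to 36 months, with exact 95% confidence intervals for the proportions.
2. These are compared with what the main trial would require. On the plan's current figures that is 2 × 171 = 342 patients before allowance for attrition.
3. The sample size recalculation is a supporting step. It uses the pre-set margin and planned or external effect rates, and takes attrition from the pilot. Any control rate from the pilot enters only with its confidence interval.
4. The pilot's observed treatment difference is not used in the recalculation.

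The cost is a few sentences. Sections 9.1 and 9.7 and the CONSORT diagram already provide for the data. The drawback is that the intervals will be wide, as Step 4 shows, and the report must say so.
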